Study design	This is a multi-center Phase II study investigating the efficacy and safety of reinfusion of tisagenlecleucel in pediatric and young adult patients with ALL who were previously treated with tisagenlecleucel and experience B cell recovery. The study will be comprised of 54 patients with 49 evaluable pediatric and young adult patients up to and including 25 years of age who have been previously infused with commercial tisagenlecleucel once and have an additional dose of commercial tisagenlecleucel available and prescribed in the course of medical practice.
Population	Patients up to and including 25 years of age with B-cell precursor acute lymphoblastic leukemia (ALL) who have been treated with commercial

	tisagenlecleucel once and have an additional dose available and prescribed to them in the course of medical practice.
Key Inclusion criteria	
 
Must have an additional unexpired dose of commercial tisagenlecleucel available which is prescribed by a physician in the course of medical practice
 
Patients who were previously treated with commercial tisagenlecleucel and present with evidence of B-cell recovery as defined by: 
 
Peripheral blood (PB) absolute B lymphocyte count <math>\geq 50/\mu\text{L}</math>, OR
 
PB B lymphocyte <math>\geq 10\%</math> of the total lymphocytes
 
 
 

Key Exclusion criteria	
 
Prior gene therapy other than tisagenlecleucel
 
Prior adoptive T cell therapy other than tisagenlecleucel
 
Active CNS involvement by malignancy
 
Active or latent hepatitis B or active hepatitis C (test within 8 weeks of screening), or any uncontrolled infection at screening
 
HIV positive test within 8 weeks of screening. False positivity should be excluded by antigen detection tests or nucleic acid tests that have been shown not to cross react with tisagenlecleucel vector.
 

Study treatment	Not applicable. A second dose (for re-infusion) of commercial tisagenlecleucel is not considered a study treatment because it is released commercially when prescribed by the treating physician in the course of medical practice.
Efficacy assessments	
 
B and T-cells by Flow Cytometry
 
CTL019 Pharmacokinetics by qPCR
 

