#### 4.5.1.3.1 Viral Reactivation

Patients with active hepatitis B or active hepatitis C or HIV positive have been excluded from clinical studies with tisagenlecleucel. Patients with prior hepatitis B or C have the potential risk of viral reactivation and the risk of fulminant hepatitis, hepatic failure and fatal outcome.

Subjects with active or prior hepatitis B, hepatitis C or HIV confirmed by serology will not be enrolled in the study; for detailed exclusion criteria see [Section 5.2](#), for serology assessment see [Table 16-1](#)

A therapeutic strategy for the management of infections is provided in [section 6.6.2.3](#)

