### 5.2 Exclusion criteria

Subjects eligible for this study must not meet **any** of the following criteria:

1. Prior gene therapy other than tisagenlecleucel

2. Prior adoptive T cell therapy other than tisagenlecleucel
3. Active CNS involvement by malignancy
4. Systemic chemotherapy or radiotherapy within 2 weeks prior to enrolment or tyrosine kinase inhibitors (for patients with Philadelphia chromosome positive ALL) within 1 week prior to enrolment.

Notes:

- Non-hematologic toxicity from prior treatment must be resolved to CTCAE grade 1 or better.
- The use of hydroxyurea is permitted for temporary control of WBC elevations in patients with aggressive disease both prior and during the first 7 days after enrolment.
- The use of corticosteroids within one week prior to enrolment is also allowed

5. Presence of active or prior hepatitis B or C as indicated by serology (for detailed criteria see [Table 16-2](#)). Serology must be repeated, if the interval between testing at Screening and tisagenlecleucel infusion exceeds 8 weeks.
6. HIV positivity as indicated by serology. Serology must be repeated, if the interval between testing at screening and tisagenlecleucel infusion exceeds 8 weeks.
7. Clinically significant acute infection confirmed by clinical evidence, imaging, or positive laboratory tests within 72 hrs prior to tisagenlecleucel infusion (e.g., blood cultures, PCR for DNA/RNA, etc.).
8. Previous or concurrent malignancy except for curatively treated non-melanoma skin cancers, in situ carcinoma (e.g. cervix, breast, bladder, prostate), and cancers in complete remission for at least 3 years and without evidence of recurrence.
9. Pregnant or nursing (lactating) women. NOTE: Women of child-bearing potential must have a negative serum pregnancy test performed within 24 hours before lymphodepletion (if performed) and prior to tisagenlecleucel infusion.
10. Women of child-bearing potential, defined as all women physiologically capable of becoming pregnant, **unless** they agree to use highly effective methods of contraception from enrollment into this study through at least 12 months after the tisagenlecleucel infusion and until CAR T-cells are no longer present by qPCR on two consecutive tests. qPCR test results will be available upon request. Highly effective contraception methods include:

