## 16 Appendices

### 16.1 Appendix 1: Eligibility based on serologic markers for hepatitis B and C:

#### Hepatitis B

1. Test for Hepatitis B surface antigen (HBsAg), Hepatitis B surface antibody (HBsAb) and Hepatitis B core antibody (HBcAb).
  2. If all of these three tests are negative, the patient is eligible.
  3. If HBsAb only is positive:
    - a. The patient is eligible in the absence of signs of hepatitis (e.g. increase of AST/ALT).
    - b. Test for HBV DNA in presences of signs of hepatitis (e.g. increase of AST/ALT).
  4. If HBsAg is positive, the patient is **NOT** eligible.
  5. If HBsAg is negative but either HBcAb or both HBcAB and HBsAb are positive, test for HBV DNA.
    - a. If HBV DNA is positive, the patient is **NOT** eligible.
    - b. If HBV DNA is negative, the patient is eligible.

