#### Hepatitis C

1. Test for Hepatitis C virus antibody (HCV Ab).
2. If HBV Ab is negative, the patient is eligible.
3. If HCV Ab is positive, test for HCV RNA.
  - a. If HCV RNA is negative, the patient is eligible.
  - b. If HCV RNA is positive, the patient is **NOT** eligible.

Patients with a history of Hepatitis B or C should be managed according to the current guidance from the American Society of Clinical Oncology (Hwang et al, 2015) and HCV Guidance from the American Association for the Study of Liver Disease-Infectious Diseases Society of America (2014-2017).

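### Patients with serological evidence of past hepatitis B or C are excluded by Sections 4.5.1.3.1 and 5.2 but eligible under Appendix 1, and the hepatitis C decision line in Appendix 1 names the wrong antibody

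*Protocol*

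**What the plan says.** Four places in the Protocol state a hepatitis eligibility rule.

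- **Section 5.2, exclusion 5:** "Presence of active or prior hepatitis B or C as indicated by serology". For detailed criteria it refers to Table 16-2.
- **Section 4.5.1.3.1:** "Subjects with active or prior hepatitis B, hepatitis C or HIV confirmed by serology will not be enrolled in the study". For the serology assessment it refers to Table 16-1.
- **Protocol summary, key exclusion criteria:** "Active or latent hepatitis B or active hepatitis C (test within 8 weeks of screening".
- **Appendix 1 (Section 16.1):** titled "Eligibility based on serologic markers for hepatitis B and C". Hepatitis B step 5 reads "If HBsAg is negative but either HBcAb or both HBcAB and HBsAb are positive, test for HBV DNA", and its second branch reads "If HBV DNA is negative, the patient is eligible". The hepatitis C list opens with "Test for Hepatitis C virus antibody (HCV Ab" and continues at step 2 with "If HBV Ab is negative, the patient is eligible". Step 3 sends HCV antibody positives to HCV RNA: a negative RNA result is eligible (3a) and a positive one is not (3b). The Appendix closes with management guidance for patients who have a history of either infection.

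Section 8.1.1 (Screening) lists the viral tests and refers to Appendix 1 for interpreting the hepatitis results. The SAP contains no hepatitis rule. It plans a listing of protocol deviations (SAP 2.3.3.6).

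**The concern.** For the same laboratory results, one part of the Protocol excludes the patient and another admits the patient. This is a safety criterion. Section 4.5.1.3.1 treats prior hepatitis B or C separately from active disease, and attaches to it a potential risk of viral reactivation, fulminant hepatitis, hepatic failure and death.

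Two sites that rely on different sections could each follow the Protocol and still decide the same case in opposite ways. A monitor who later checks such a patient cannot say whether the enrolment was a deviation until someone decides which text applies.

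**Working it through.** No arithmetic applies. The check takes each serology profile through each rule, then follows each cross-reference.

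**Profiles**

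| Profile | Exclusion 5 and 4.5.1.3.1 | Appendix 1 | Summary |
|---|---|---|---|
| HBsAg−, HBcAb+, HBV DNA− | Excluded as prior hepatitis B by serology | Eligible (hepatitis B step 5b) | Unclear: latent is not defined |
| HCV Ab+, HCV RNA− | Excluded as prior hepatitis C by serology | Eligible (hepatitis C step 3a) | Not excluded: names only active C |
| HBsAg+, or HBcAb+ with HBV DNA+ | Excluded | Not eligible | Excluded |
| HCV Ab+, HCV RNA+ | Excluded | Not eligible at step 3b, but eligible at step 2 if HBV Ab is negative and the line is read literally | Excluded |
| HCV Ab−, HBV Ab+ | No hepatitis C ground for exclusion | No step in the hepatitis C list gives an outcome | No hepatitis C ground for exclusion |
| HBsAb+ only, no signs of hepatitis | Not clearly prior infection | Eligible (hepatitis B step 3a) | Not clearly named |

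The first two rows are direct contradictions. Both are profiles of past infection. The third row is consistent throughout. The fourth and fifth go wrong only through the hepatitis C step 2 line. The last is not a clear conflict, because HBsAb alone need not mean past infection.

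**Hepatitis C list.** Step 1 orders HCV antibody and step 3 acts on HCV antibody. Only step 2, between them, names an HBV antibody. Two hepatitis B antibodies (HBsAb and HBcAb) are tested, and step 2 does not say which is meant.

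**Cross-references**

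- Exclusion 5 points to Table 16-2, which covers the recording of concomitant medication and laboratory data. It holds no hepatitis criteria.
- Section 4.5.1.3.1 points to Table 16-1, which covers adverse event reporting. It holds no serology criteria.
- Section 8.1.1 points to Appendix 1. This pointer works, but it concerns interpretation of results and does not say that Appendix 1 prevails over exclusion 5.

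**Tests listed.** Table 8-4 names HBsAg, HBsAb, HBcAb and HCVAb. The HBV DNA and HCV RNA tests on which Appendix 1 turns are not in that table. Appendix 1 hepatitis B step 3b also orders HBV DNA, for patients positive for HBsAb alone who have signs of hepatitis, but gives no eligibility outcome.

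**The case against.** The best reply is that exclusion 5 is shorthand and Appendix 1 defines it. Exclusion 5 defers to detailed criteria, Appendix 1 is the only place where such criteria appear, its title says that it concerns eligibility, and the screening section sends sites there. On that view the table number in exclusion 5 is only a broken link. This is a reasonable reading, and it would be wrong to infer that no pointer to Appendix 1 works. It does not settle the matter, however. Section 4.5.1.3.1 separately says that prior cases will not be enrolled, in terms that cover profiles Appendix 1 admits, and the summary matches neither.

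Three stronger readings are tempting and are not supported.

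- A reader might infer that the Appendix tests for the wrong virus. It does not: step 1 orders HCV antibody, as do Section 8.1.1 and Table 8-4. The slip is in the step 2 condition and is probably a typing error.
- A reader might infer that all hepatitis eligibility is contradictory. Apart from the step 2 slip, active infection is excluded consistently. The conflict concerns past infection.
- A reader might infer that the conflict decides Per-Protocol membership. Protocol 12.1.5 leaves the criteria for exclusion from that set to be finalised before database lock, and nothing says that this discrepancy would count. The primary analysis uses the Full Analysis Set, meaning all re-infused patients. The current SAP defines no Per-Protocol Set (2.2) and marks sensitivity analyses as not applicable (2.6.4.1).

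It is also fair to say that the practical reach is small. The study closed with 5 of a planned 54 patients enrolled (SAP 2.6), and the documents do not show that any of them had either profile.

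**Conclusion.** The contradiction stands for two profiles: HBsAg negative, HBcAb positive, HBV DNA negative; and HCV antibody positive, HCV RNA negative. Each is excluded in two places and eligible in a third, and the summary adds a wording that agrees with neither. The step 2 line separately makes the hepatitis C list inconsistent with itself when read literally.

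This rests on reading prior infection indicated by serology in its plain sense, which includes a positive HBcAb or HCV antibody. If Appendix 1 was meant to narrow that sense, the Protocol does not say so.

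The effect is on consistency of enrolment and on classification of deviations for a safety criterion. It has no bearing on the sample size, and no planned analysis is shown to depend on it. The documents give no frequency for either profile, so the number of enrolled patients affected lies between 0 and 5 and may well be 0. No view is taken here on which eligibility rule is clinically right.

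**What to change.** - Reconcile the Protocol summary, Section 4.5.1.3.1, exclusion 5 and Appendix 1 so that each serology profile has one stated outcome, including hepatitis B step 3b, which now has none. The choice of rule belongs to the sponsor's clinical team.
- Point the cross-references in exclusion 5 and Section 4.5.1.3.1 to the place that holds the rule.
- Make the antibody named in hepatitis C step 2 consistent with steps 1 and 3.
- Because the study is closing, state in the clinical study report which rule was applied when eligibility deviations were listed, and whether any enrolled patient had either of the two profiles.

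The cost is Protocol wording and a short statement in the report. No new data and no change to any analysis are needed.

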## 6 Treatment

### 6.1 Study treatment

A second dose of commercial tisagenlecleucel is not considered study treatment because it is released commercially to the treating physician when it is prescribed in the course of medical practice. The doses available for reinfusion were previously manufactured for each individual patient as commercial product and a physician can request an additional dose for commercial release at any time, prior to product expiration and subject to availability.

Tisagenlecleucel is an autologous cellular immunotherapy product that is comprised of CD3+ T-cells that have undergone *ex vivo* T-cell activation, gene modification, expansion and formulation in infusible cryomedia. The transgene to be expressed via lentiviral vector transduction is a CAR targeted against the CD19 antigen. The CAR contains a murine scFv that targets CD19 linked to a transmembrane region derived from the CD8 receptor, which is linked to an intracellular bipartite signaling chain of TCR- $\zeta$  (or CD3- $\zeta$ ) and 4-1BB intracellular signaling domains. The extracellular scFv with specificity for CD19 is derived from a mouse monoclonal antibody. T-cells which are enriched from a subject leukapheresis unit are expanded *ex vivo* using commercially available magnetic beads that are coated with anti-CD3 and anti-CD28 monoclonal antibodies. The cells are transduced with the CD19 CAR lentiviral vector which ensures that only peripheral white blood cells enriched for lymphocytes are exposed to the vector. The residual non-integrated vector is washed away during the process. Tisagenlecleucel will be expanded *ex vivo*. At the end of the culture, the tisagenlecleucel is washed, concentrated, and cryopreserved. Results from a release testing procedure are required prior to release of the product for infusion.

For details please refer to the [Kymriah Package Insert] and the current version of the [tisagenlecleucel Investigator's Brochure].

**Table 6-1 Drug Supply**

Drug	Pharmaceutical Dosage Form	Route of Administration	Supply Type	Sponsor (global or local)
A Commercially available second dose of tisagenlecleucel prescribed at the discretion of the treating physician in the course of medical practice	Cell dispersion	Intravenous use	Open label, Commercial; infusion bags	Local

#### 6.1.1 Investigational and Control Drugs

Not applicable

### **6.1.1.1 Decentralized Clinical Trial Model (US sites only)**

Not applicable

### **6.1.1.2 Bio-batch retention samples**

Not applicable

### **6.1.2 Pre-infusion evaluation**

If any of the following criteria is met tisagenlecleucel infusion must be delayed until resolution to grade 1. If the period of delay is more than 4 weeks from completing lymphodepletion and there is no significant cytopenia (see [Section 6.1.6](#)) Lymphodepletion should be repeated, and these criteria will need to be re-checked prior to tisagenlecleucel infusion.

1. Rapidly progressing primary disease (e.g. leukemia/lymphoma)
2. Clinical evidence of CNS involvement by primary disease
3. Laboratory abnormalities that, in the opinion of the investigator, may impact subject safety or the subjects' ability to receive tisagenlecleucel.
4. Following clinical abnormalities:
  - Pulmonary: Requirement for supplemental oxygen to keep saturation greater than 90% or presence of progressive radiographic abnormalities on chest x-ray
  - Cardiac arrhythmia not controlled with medical management
  - Hypotension requiring vasopressor support
  - Clinically significant active infection confirmed by clinical evidence, imaging, or positive laboratory tests (e.g., blood cultures, PCR for DNA/RNA, etc.). NOTE: All viral serology must be repeated, if the interval between testing prior to lymphodepletion and tisagenlecleucel infusion exceeds 8 weeks.
5. A significant change in clinical status that would, in the opinion of the investigator, increase the risk of adverse events associated with tisagenlecleucel
6. Toxicities from chemotherapy (including lymphodepletion).
7. Prohibited medications as described in [section 6.2.1](#)
8. Positive influenza test within 10 days prior to tisagenlecleucel infusion (please refer to [Table 8-1](#)). If the subject is positive for influenza, oseltamivir phosphate or zanamivir should be administered for 10 days as preventative treatment (see Tamiflu® or Relenza® package insert for dosing). The subject must complete their 10 day preventative treatment course **prior** to receiving tisagenlecleucel. The test does not need to be repeated prior to tisagenlecleucel infusion however if flu-like or respiratory signs and symptoms are present, tisagenlecleucel infusion should be delayed until the subject is asymptomatic. For subjects residing in the United States, Canada, Europe and Japan, influenza testing is required during the months of October through May (inclusive). For subjects residing in the southern hemisphere such as Australia, influenza testing is required during the months of April through November (inclusive). For subjects with significant international travel, both calendar intervals above may need to be considered.

9. Live vaccines must not be used in tisagenlecleucel recipients for at least 6 weeks prior to the start of lymphodepleting chemotherapy, during tisagenlecleucel treatment, and until immune recovery following treatment with tisagenlecleucel.
10. Women of child-bearing potential must have a negative serum pregnancy test performed within 24 hours prior to tisagenlecleucel infusion.

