### 6.1.4 Additional study treatments

#### Lymphodepletion

If patients have a White Blood Cell (WBC) count  $\leq 1,000$  cells/ $\mu$ L within one week prior to tisagenlecleucel infusion, lymphodepleting chemotherapy is **NOT** required.

The availability of tisagenlecleucel must be confirmed prior to starting the lymphodepleting regimen.

Tisagenlecleucel should be infused 2 to 14 days after lymphodepletion depending on the lymphodepleting regimen. If there is a delay of more than 4 weeks between completing lymphodepleting chemotherapy and the infusion and the WBC count is  $>1,000$  cells/ $\mu$ L, the patient should be re-treated with lymphodepleting chemotherapy prior to receiving tisagenlecleucel. The preferred regimen is as follows:

- Fludarabine (30 mg/ $m^2$  intravenously (i.v.) daily for 4 days)
- Cyclophosphamide (500 mg/ $m^2$  i.v. daily for 2 days starting with the first dose of fludarabine)

Side effects of fludarabine include severe neurological events of seizure, agitation, blindness, coma and death. Instances of life-threatening and sometimes fatal autoimmune phenomena such as hemolytic anemia, autoimmune thrombocytopenia/thrombocytopenic purpura (ITP), Evans syndrome, and acquired hemophilia have been reported to occur after one or more cycles of treatment with fludarabine phosphate injection. Fludarabine may also severely decrease bone marrow function (Fludarabine full prescribing information).

Cyclophosphamide can cause cardiac dysfunction. Acute cardiac toxicity has been reported with doses as low as 2.4 g/ $m^2$  to as high as 26 g/ $m^2$ , usually as a portion of an intensive antineoplastic multi-drug regimen or in conjunction with transplantation procedures. High doses of cyclophosphamide led in a few instances to severe, and sometimes fatal, congestive heart failure after the first dose. Severe marrow suppression is seen and occasional anaphylactic reactions have been reported. Hemorrhagic cystitis, pulmonary toxicity (pneumonitis, pulmonary fibrosis and pulmonary veno-occlusive disease leading to respiratory failure) and veno-occlusive liver disease may occur (Cyclophosphamide full prescribing information).

*Alternative lymphodepletion for pediatric studies:*

- Cytarabine 500 mg/ $m^2$  i.v. daily for 2 days and
- Etoposide 150 mg/ $m^2$  i.v. daily for 3 days starting with the first dose of cytarabine

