**Table 8-1 Assessment Schedule**

Period	Category	Screening	Treatment			End of Study	
Visit Name		Screening	Enrollment	Assessment Period		End of Study	
Day/Week/Month		-28 to -1	D1 	D28±7	M3±14	M6±14	M12±14
Obtain informed consent	D	X					
Demography	D	X					
Inclusion/exclusion criteria	D	X					
Relevant medical history/ current medical history	D	X					
Physical Exam	S	X	X	X	X	X	X
Height	D	X					
Weight	D	X	X	X	X	X	X
Vital Signs	D	X	X	X	X	X	X
Karnofsky/Lansky Performance Scales	D	X					X
Serum Pregnancy Test (Table 8-4)	S	X	X				X
Urine Pregnancy Test (Table 8-4)	S			X	X	X	
Hematology	D	X	X	X	X	X	X
Chemistry	D	X	X	X	X	X	X
HIV & Hepatitis B & C testing	D	X					
Serum immunoglobulin levels (IgG, IgA, IgM)	S	X					
Rapid influenza test	D		X 				
B & T-Cells by Flow Cytometry – [REDACTED]	D		X	X	X		X
CTL019 PK by qPCR- NAVIGATE	D		X	X	X		X
[REDACTED]							
Bone Marrow Aspirate or Biopsy	D	X		X	X 	X 	X 
Re-infusion of prescribed, commercially available tisagenlecleucel	D		X				

Period	Category	Screening	Treatment			End of Study
Visit Name		Screening	Enrollment	Assessment Period		End of Study
Day/Week/Month	-28 to -1	D1 	D28±7	M3±14	M6±14	M12±14
Prior/Concomitant Medications	D	X	X	X	X	X
Adverse Events (refer to Table 16-1 )	D	X	X	X	X	X

 All Day 1 assessments should be performed prior to infusion with the exception of vital signs which will be monitored before and after infusion  
 Optional assessments to be performed if clinically indicated  
 Must be performed within 10 days of infusion during the months of October through May

X = assessment is required

D = assessment to be recorded in clinical database or received electronically from a vendor

S = assessment to be recorded in the source documentation only

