### 8.1.5 Treatment

#### Infusion visit (D1)

On the day prior or day of the scheduled infusion, patients will undergo a physical exam (including weight and vital signs). A blood sample will be collected pre-infusion for PK

assessment, B & T cells by Flow Cytometry [REDACTED]. In addition, a serum pregnancy test will be performed on women of child bearing potential confirming a negative pregnancy result. Adverse events and prior/concomitant medications will be reviewed.

All patients must undergo a rapid influenza diagnostic test (only during the months of October through May) within 10 days prior to the planned infusion. If the patient is positive for influenza, he/she should complete a full course of oseltamivir phosphate or zanamivir as described on the label (see Tamiflu® or Relenza® package insert for dosing). The patient must complete their full course of treatment **prior** to infusion. The test does not need to be repeated prior to infusion however if influenza sign and symptoms are present, infusion should be delayed until patient is asymptomatic.

For patients that require lymphodepleting chemotherapy, tisagenlecleucel infusion will begin 2 to 14 days after completion. The total window between informed consent and tisagenlecleucel infusion must not exceed 16 weeks.

Tisagenlecleucel transduced T-cells will be given as prescribed and in accordance with the [Kymriah Package Insert]. Vital signs will be monitored before and following infusion. In addition, adverse events and prior/concomitant medications will be reviewed.

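### The protocol gives an influenza-positive patient two different antiviral courses to finish before re-infusion, and its testing calendars conflict for southern-hemisphere residents

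*Protocol*

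**What the plan says.** Three places in the current protocol text govern influenza before re-infusion.

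- **Protocol 6.1.2, item 8.** After a positive test within 10 days before infusion, "oseltamivir phosphate or zanamivir should be administered for 10 days as preventative treatment", and this must be finished before infusion: "The subject must complete their 10 day preventative treatment course". Flu-like or respiratory signs delay infusion further. Testing runs October to May for residents of the US, Canada, Europe and Japan, and April to November for the southern hemisphere. For travellers: "For subjects with significant international travel, both calendar intervals above may need to be considered". The item refers the reader to Table 8-1.
- **Protocol 8.1.5, Infusion visit (D1).** After a positive test, "he/she should complete a full course of oseltamivir phosphate or zanamivir as described on the label". This too comes before infusion: "The patient must complete their full course of treatment". Signs of influenza delay infusion further. Every patient is tested, but only in October to May.
- **Protocol Table 8-1, footnote 3.** "Must be performed within 10 days of infusion during the months of October through May". There is no regional variant.

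On timing after lymphodepletion, Protocol 6.1.4 says: "Tisagenlecleucel should be infused 2 to 14 days after lymphodepletion depending on the lymphodepleting regimen". Section 8.1.5 repeats the 2 to 14 days. The opening of 6.1.2 and the text of 6.1.4 also provide for delays of more than 4 weeks after lymphodepletion, when it should be repeated under stated conditions.

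**The concern.** Both antiviral rules are mandatory, apply to the same patient, and control the same step. One fixes the length at 10 days and calls the course preventative. The other leaves the length to the label and calls it treatment. No section says which prevails. A site reading 6.1.2 and a site reading 8.1.5 could each believe it had complied and yet clear the same patient on different dates.

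The testing rule has a similar problem. A southern-hemisphere site that follows 6.1.2 to Table 8-1, as directed, finds a footnote that contradicts the calendar it has just read.

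At stake are a pre-infusion safety check in an immunosuppressed population of up to 25 years of age and the consistent classification of protocol deviations, which SAP 2.3.3.6 lists.

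**Working it through.** The plan states no figure to reproduce. The check compares the texts and adds two small counts.

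**1. The rules side by side**

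| Element | 6.1.2 item 8 | 8.1.5 | Table 8-1 fn 3 |
|---|---|---|---|
| Course length | 10 days | per label, no number | not stated |
| Purpose named | preventative | treatment | not stated |
| Must finish before infusion | yes | yes | not stated |
| Symptoms that delay | flu-like or respiratory | influenza | not stated |
| Calendar | by region | Oct-May, all patients | Oct-May |

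Section 6.1.2 also cites the package inserts, but for dosing; the 10 days stay fixed.

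**2. Calendar**

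October-May is the set {10, 11, 12, 1, 2, 3, 4, 5}. April-November is {4, 5, 6, 7, 8, 9, 10, 11}. For a southern-hemisphere resident:

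- both require the test in April, May, October and November: 4 months;
- only 6.1.2 requires it in June to September: 4 months;
- only 8.1.5 and Table 8-1 require it in December to March: 4 months.

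Disagreement: 4 + 4 = 8 of 12 months. For residents of the four northern regions named in 6.1.2 the sets are identical.

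**3. Date of re-infusion**

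Inputs: the positive test falls *t* days before planned infusion, with *t* at most 10 (6.1.2, Table 8-1). The 6.1.2 course is 10 days. The label course is *L* days, which the documents do not give; 3 to 10 is assumed for illustration. Also assumed: the course starts on the test day, infusion follows on the first day after it, and there are no symptoms.

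Delay under 6.1.2 = max(0, 10 - *t*). Delay under 8.1.5 = max(0, *L* - *t*). The last four columns show the first minus the second, in days.

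| *t* | Delay, 6.1.2 | *L* = 3 | *L* = 5 | *L* = 7 | *L* = 10 |
|---|---|---|---|---|---|
| 1 | 9 | 7 | 5 | 3 | 0 |
| 3 | 7 | 7 | 5 | 3 | 0 |
| 5 | 5 | 5 | 5 | 3 | 0 |
| 7 | 3 | 3 | 3 | 3 | 0 |
| 10 | 0 | 0 | 0 | 0 | 0 |

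Example, *t* = 1 and *L* = 5: (10 - 1) - (5 - 1) = 9 - 4 = 5 days.

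**4. Lymphodepletion window**

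Take lymphodepletion completed on Day -8 and a positive test on Day -1, with planned infusion as Day 1 and no Day 0 (the convention of SAP 2.1.1.7). A 10-day course started on Day -1 has its tenth day on Day 9. Day -8 to Day 1 is 8 days and Day 1 to Day 9 is 8 days, so Day 9 is 16 days after lymphodepletion. The first day after the course, Day 10, is 17 days after. Both are past 14 days and well short of 4 weeks (28 days).

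**The case against.** The strongest reply is that most of the practical consequence is either unproven or already provided for. Taken in turn:

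- **Different dates.** A reader might infer that two compliant sites would infuse the same patient on different dates. The documents support only that they could. The gap is zero if the label course is 10 days, and zero for a test 10 days before infusion with any course up to 10 days. If the label course is 10 days or less, a site that waits 10 days has waited at least as long as either section asks. This stands as a limit on size; it does not reconcile the two texts.
- **Lymphodepletion.** A reader might infer that an influenza delay collides with the 2 to 14 day window and that nothing addresses it. That is not supported. Influenza is one item in a list of delay criteria, so delay is the rule's purpose, and 6.1.2 and 6.1.4 both foresee delays beyond the window. What remains is narrow: 8.1.5 repeats 2 to 14 days without the delay provision.
- **Travellers.** A reader might infer that a traveller in June to September must be tested under one section and not under the other. The clause in 6.1.2 is permissive, so there is no firm conflict for this group.
- **Calendar and date.** The calendar decides whether a test is done. It moves the infusion date only through a positive result. The documents do not list participating countries, so the number of southern-hemisphere patients is unknown.
- **Symptoms.** Other provisions also hold back patients with significant infection: 6.1.2 item 4, exclusion criterion 7 and 6.6.2.3. The difference in symptom wording therefore has little practical effect.

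**Conclusion.** The concern holds as an inconsistency between sections of the current protocol. Section 6.1.2 item 8 and section 8.1.5 set different mandatory courses for the same influenza-positive patient. The symptom conditions differ in wording. The testing calendars contradict each other for southern-hemisphere residents in 8 of 12 months.

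The effect on the permitted re-infusion date is possible but cannot be fixed from the documents. Under the assumptions above it ranges from 0 to 7 days over the cases tabulated, and it vanishes if the label course is also 10 days. The wording and calendar conflicts remain even then.

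The matter is operational. A reader might infer a threat to the efficacy result, but the point touches no endpoint definition, analysis set, sample size or alpha. The trial also closed early with 5 of a planned 54 patients enrolled (SAP 2.6 and 4), which limits the practical reach.

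**What to change.** Reconcile Protocol 6.1.2 item 8, 8.1.5 and Table 8-1 footnote 3 into one rule: one antiviral course, one symptom condition and one testing calendar. State it in one place and cross-refer to it from the other two. Align the 2 to 14 day statement in 8.1.5 with the delay provisions already in 6.1.2 and 6.1.4.

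Which course, symptom condition or calendar is right is for the sponsor's clinical team; this review takes no position.

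The cost is protocol wording only, with no new procedure. As the trial has closed, the remaining use is to record which rule applied when classifying any influenza-related delay or missed test in the deviation listing, and to avoid carrying the conflict into a later protocol.
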